Electrotherapy, or electrical stimulation delivered to target muscles using an external stimulator connected to electrodes and surface hydrogel pads, has been widely used for treatment, rehabilitation, and training purposes. Electrotherapy interventions, such as neuromuscular electrical stimulation (NMES) and functional electrical stimulation (FES), have resulted in improvements in gait performance^{13,14} and increased quadriceps strength^{15,16} to counteract muscle decline. This is reasonable as NMES produces muscular contractions³⁸, and FES provides stimulation with a targeted movement, such as walking, to mimic normal voluntary kinematics³⁹. On the contrary, there are studies that do not support NMES for pain management¹⁷ and objective measures of function¹⁸. However, those studies explored the application of NMES alone and excluded studies combining electrical stimulation interventions with exercise. Additionally, there are limited studies exploring FES in the KOA population despite its positive effects in walking speed^{40, 41}, lower limb kinematics⁴¹, and muscle mass and strength⁴² in the stroke and multiple sclerosis communities. Pairing electrical stimulation with exercise has been employed to improve muscle activation in the affected leg of hemiplegic patients¹⁹ and provide a greater stimulus for muscle hypertrophy than stimulation or exercise alone when voluntary activation deficit is present²⁰, thereby confirming the value of combined electrotherapy for those with impaired limbs. This combined intervention was also supported as an effective alternative to relieve pain, increase quadriceps strength, improve physical function and functional performance in patients with KOA who have difficulty performing an exercise program²¹. Although there are inconsistencies regarding electrotherapy for the KOA community, there should be a recognition

and utilization of electrotherapy combined with activities to promote physical activity and better manage some symptoms associated with the disease.

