A sample size of 32 participants was calculated to be sufficient for a two-tailed significance level of 5% and a power of 80% (Appendix A). This was adjusted to 45 participants with knee osteoarthritis to allow for dropouts. Recruitment for this study will be conducted using a recruitment flyer and through the CIONIC website. Recruitment will be based on a first come

basis. Interested participants will complete a questionnaire to be reviewed according to the inclusion and exclusion criteria. Responses will then be reviewed, and prospective participants will be invited to schedule a virtual meeting with a study staff member who will screen the prospective subject for an understanding of the study and for their voluntary participation. All participants will be assigned a unique number using a computer random number generator and randomly assigned to a group by a researcher. All participants will receive their assigned intervention at their first lab visit.

Inclusion Criteria

- Persons with knee osteoarthritis between the ages of 22 and 75
- Ability to walk a duration of 30 minutes per walking session (with or without an assistive device), for three days per week
- Able to tolerate the device for up to 1 hour per lab session
- No recent change in medication or exacerbation of symptoms over the last 60 days
- Radiographic KOA K&L grade 2 or 3 or physician diagnosed mild or moderate KOA if radiographic imaging is not available
- No hyaluronic acid or cortisone injection into knees in previous 12 months

Exclusion Criteria

- Lower motor neuron disease or injury (e.g. peripheral neuropathy) that may impair response to stimulation
- Absent sensation in the impacted or more impacted leg

- Inadequate response to stimulation, as defined as inability to achieve muscle contraction or tolerate stimulation
- Inability to ambulate with the sleeve in place of an ankle foot orthosis (AFO)/knee ankle foot orthosis (KAFO) if utilized
- Use of FES devices in the past year
- Demand-type cardiac pacemaker or defibrillator
- Malignant tumor in the impacted or more impacted leg
- Existing thrombosis in the impacted or more impacted leg
- Fracture or dislocation in the impacted or more impacted leg that could be adversely affected by motion from stimulation
- History of knee surgery
- History of other types of arthritis
- History of neurological disease
- History of seizures or diagnosed with epilepsy/seizures
- Current pregnancy

Methodology

Overview of Study

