This study is a randomized controlled trial. Figure 2 depicts a flow diagram of the study design. Participants will be screened for eligibility through a questionnaire, and after study details are explained and consent is obtained, they will be invited to the study site. Assessments will be conducted at CIONIC Inc., and involve approximately 45 patients for a 12 week study period.

CIONIC

CIONC FOR ORTHOPEDICS

All subjects will be assigned an electrical stimulation system to wear on the most impacted leg and be prescribed a home-based exercise and walking program. Subjects will be randomly assigned into three groups: (a) control; (b) NMES+; (c) NMES+FES. The control group will not receive stimulation for the exercise and walking program, whereas subjects in NMES+ will receive stimulation during exercises, and subjects in the NMES+FES group will receive stimulation during exercises and walking. Outcome measures will be assessed at baseline, 6 weeks after baseline, and end of study (Table 2). Equipment and additional feedback will be collected at the end of study. These three groups will be analyzed using several outcome measures. Primary outcome measures of the study are quadriceps strength, perceived functional capacity, self-reported pain, and walking performance. Secondary interest will be adherence to program, thigh muscle volume, functional ability of the lower limb, and quality of life. The CIONIC system will be used to track adherence (duration of sessions, frequency of use).

[figure not shown]

Figure 2: Study flow

Table 2: Study overview

Comparison Groups	Treatment Schedule	Timing and Outcome Measures
Control (unstimulated exercise and walking)	Exercise: 5x/week for 12 weeks Progression every 3 weeks	At baseline, midpoint and end of study: Quadriceps strength Perceived functional capacity Self-reported pain Walking performance Thigh muscle volume Functional ability of lower limb Quality of life EMG activity
NMES+ (NMES+exercise and unstimulated walking)	Walking: 10 min, 3x/week for 12 weeks Progression up to 30 min by end of study	Weekly: Adherence to program
NMES+FES (NMES+exercise and FES+walking)		

Participant Identification, Recruitment & Informed Consent

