CIONIC researchers will follow a recruitment plan (Figure 3). CIONIC will post a recruitment flyer on their website and interested participants may send an email directly to [contact]. CIONIC may also recruit directly from physical therapy providers and osteoarthritis advocacy groups through a recruitment flyer with their permission. The study staff will email interested candidates a screening questionnaire to assess for study eligibility. CIONIC researchers will then contact qualified candidates to set up a Zoom meeting to explain study details, address risks and benefits, and answer questions. Those who opt to participate in the study will receive an electronic consent form via DocuSign for their review and electronic signature. A member of the CIONIC team will guide the participant through the informed consent document, and answer concerns. Participants who sign the informed consent document will receive a copy for their records and proceed with the study. All forms will be stored on a secure server. After consent is obtained, the CIONIC researchers will schedule the subject to report to the study site for initial assessment.

[figure not shown]

Figure 3: Recruitment plan

Participant Capacity and Comprehension

The study's inclusion criteria and recruitment plan may include individuals with decision making impairments and/or language and communication impairments. To mitigate this, the video conference call will further screen and determine if the severity of their impairments will require additional safeguards or if the interested party will need to be excluded from the study.

Lab Visits

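### The exclusion for earlier stimulation names only FES devices, although NMES is the component both active arms share, and outside NMES is neither barred nor recorded during the study

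*Combined protocol and SAP*

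**What the plan says.** Under Participation Selection and Randomization, the exclusion list has one line on earlier stimulation: "Use of FES devices in the past year". The other limits on earlier treatment cover medication change or symptom flare (60 days) and knee injections (12 months). NMES, other muscle stimulators and physiotherapy do not appear.

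The background distinguishes the two modalities: "NMES produces muscular contractions³⁸, and FES provides stimulation with a targeted movement, such as walking". Overview of Study builds the arms on that distinction: "subjects in NMES+ will receive stimulation during exercises, and subjects in the NMES+FES group will receive stimulation during exercises and walking". Table 2 labels the exercise stimulation in both active arms as NMES and reserves FES for walking. For the comparator, "The control group will not receive stimulation for the exercise and walking program". That sentence covers the study programme and says nothing about stimulation obtained elsewhere.

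On recruitment, besides the flyer and the sponsor's website, "CIONIC may also recruit directly from physical therapy providers and osteoarthritis advocacy groups". On data, the other information collected at entry includes type and dosage of medication, but not earlier or current stimulation or therapy. Adherence is taken from the study sleeve's usage log.

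**The concern.** Objective 1 compares stimulation-assisted programmes with conventional exercise. That comparison is clearest when controls receive no stimulation of the kind under test and when participants have not recently been trained with it. The protocol protects against earlier FES, which only one arm receives, and is silent on NMES, which both active arms receive.

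Three things are at stake:

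- **Dilution.** A control who uses NMES outside the study receives part of what the trial withholds. A stimulated participant who does so largely duplicates what the trial already supplies.
- **Chance imbalance.** In small arms, a handful of users can fall unevenly.
- **Before/after tests.** The analysis section plans paired tests within each condition. Randomisation does not protect these, so outside NMES during the 12 weeks enters the measured change directly.

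If use is not recorded, none of this can be examined afterwards.

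**Working it through.** **Does any other text close the gap?**

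- *Eligibility.* The screening questionnaire is reviewed against the listed criteria, and none of them names NMES.
- *During the study.* No section prohibits outside stimulation, so its use would not count as a protocol deviation. Study Withdrawal allows removal of someone who needs additional or different treatment. That rule is discretionary, applies after entry, and does not address treatment already under way.
- *Data.* Entry data cover medication only, and the usage log sees only the study sleeve.
- *Analysis.* The t-tests, ANOVA and non-parametric alternatives specify no covariate for outside stimulation.

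Nothing closes it.

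**The plan's own figure.** Appendix A uses an effect size of 0.71 for WOMAC function, alpha 0.05 (two-sided) and power 0.8, and gives 32 for comparing group A with group B. By the normal approximation, n per arm = 2 × (1.960 + 0.842)² / 0.71² = 2 × 7.85 / 0.5041 = 31.1, which rounds up to 32. The two-sample t solution is 32.13. The figure reproduces as a per-arm number.

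**Dilution (illustration).** Let f be the fraction of controls using outside NMES and e its efficacy relative to trial NMES, from 0 to 1. Assume outside NMES adds nothing in the stimulated arms. The expected difference is then 0.71 × (1 − f × e). Power is for a two-sided 5% two-sample t-test with 15 per arm (45 / 3, assuming equal allocation and no dropout).

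| f × e | Effect | Power, 15 per arm | n per arm for 80% power |
|---|---|---|---|
| 0 | 0.710 | 47% | 33 |
| 0.10 | 0.639 | 39% | 40 |
| 0.20 | 0.568 | 32% | 50 |
| 0.30 | 0.497 | 26% | 65 |

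At f = 20% (3 of 15 controls), e between 0 and 1 gives f × e between 0 and 0.20. The effect is then 0.57 to 0.71, and power is 32% to 47%.

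**Chance imbalance (illustration).** If users are 10%, 20% or 30% of entrants, binomial counts in two arms of 15 differ by 3 or more with probability 12%, 25% or 32%.

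No value of f or e is given in the documents. The 0.71 is the planning value for WOMAC function only. Appendix A uses 0.41 for pain and gives none for quadriceps strength.

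**The case against.** **The term may be read broadly.** The protocol uses FES loosely for the whole system. The Figure 1 note describes FES electrode arrays and FES settings on a sleeve that delivers both modes, and Aim 1 speaks of validating FES although both active arms receive NMES. Staff might therefore take FES devices to mean muscle stimulators in general. This stands as a possibility, and it is why the point is conditional. It does not remove the point: the background and the arm names separate the modalities, and a screening criterion should not depend on which usage the screener has in mind.

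**Randomisation spreads users across arms.** This also stands. A reader might infer systematic bias, but the documents do not support that. If outside NMES added fully to trial NMES and uptake were equal in all arms, the expected between-arm difference would not change. Dilution requires that it duplicates trial NMES, or that controls use it more.

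**Exposure is unknown.** A reader might infer that recruitment targets physiotherapy patients, so that some use is near certain. The text makes physical therapy providers an optional route, by flyer and with their permission. No rate of use is given.

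**Physiotherapy.** A reader might extend the point to an exclusion for current physiotherapy or strengthening. That does not follow. All arms are prescribed the same exercise, stable background care is a legitimate choice, and the dilution formula does not apply to it. The 60-day medication criterion is no model either, because it permits stable treatment and bars recent change.

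**Conclusion.** The gap is real but modest. Taking the protocol's own distinction at face value, recent or current users of leg NMES are eligible for every arm, including the unstimulated control, and their use during the 12 weeks is neither restricted nor recorded. The consequences are dilution, chance imbalance and contaminated within-arm tests.

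The size cannot be determined from the documents. The range of 0.57 to 0.71 at f = 20% rests on an assumed rate, on outside NMES duplicating trial NMES in the stimulated arms, and on 0.71 being the right starting effect. Its lower end also requires outside NMES to be as effective as the trial's. A loss of one fifth of the contrast is therefore the upper end of an illustration, not an estimate. It matters because power at 15 per arm is only 47% before any dilution. The change is worth making because it is cheap and because unrecorded use cannot be recovered later.

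**What to change.** - Extend the existing exclusion line, with its one-year window, to NMES and other electrical muscle stimulation of the leg, and add the item to the existing screening questionnaire.
- Apply the same restriction to non-study stimulation during the 12 weeks, and record any such use at the three lab visits.
- Record current knee physiotherapy at baseline and at the later visits. Whether to restrict it is for the sponsor to decide.

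The cost is one amended criterion, one sentence on the study period, one screening item and a short entry on the visit forms. A few candidates would become ineligible, possibly more if the sponsor uses the optional route through physical therapy providers.

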The study will be explained to the participants and written informed consent will be obtained before the initial lab visit. Physical measurements, performance tests, and questionnaire responses will be collected at three lab visits: initial, study midpoint (6 weeks), and end of study (12 weeks). Physical measurements will include height, weight, and thigh circumference of the impacted leg. If subjects report bilateral compromised legs, the most impacted/painful leg will be measured. Participants will be asked to complete four performance tests (maximal voluntary isometric contraction of the quadriceps, Five Times Sit to Stand Test (FTSST), 10-meter Walk Test (10mWT), and the 6-Minute Walk Test (6MWT)) and three questionnaires (Western Ontario/McMaster Universities Osteoarthritis Index physical function (WOMAC-PF) subscale, WOMAC-pain, and the Short Form-36). Order of the tasks at the lab visits are as follows: maximal voluntary isometric contraction of the quadriceps, FTSST, 10mWT, WOMAC-PF, 10mWT, WOMAC-pain, 6MWT, Short Form-36, and 6MWT. Instruction will be provided to the participants before beginning a new task, and the researchers will periodically gauge the subjects for a need for a break and understanding of the task. For the walking tests, subjects will be fitted with the electrical stimulation system to collect EMG/kinematic data, and depending on the subject's group assignment, stimulation may or may not be enabled. All subjects will be provided with and instructed to wear the electrical stimulation system for the subsequent 12 weeks. All subjects will be taught how to navigate the supporting app and receive a user manual on how to operate/care for the system. Subjects assigned to receive stimulation will be taught how to adjust parameters of the device using the supporting app. All participants will receive a handout explaining the exercise, and a calendar for the exercise and walking program (Appendix

B). Subjects will be informed to perform the exercise and walking program in an area free from obstacles. Lab visits may be up to 90 minutes in duration.

Exercise and Walking Program

The participants will wear the device during the 12-week exercise and walking program. This may range from 1 minute to 35 minutes per day (Appendix B).

Exercise Program

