The WOMAC-PF is a 17-item questionnaire that measures the impact of KOA on daily physical activities in the past 48 hours²⁶. Scores on the WOMAC-PF range from 0 to 68, with high scores indicative of worse functional limitations²⁶. The minimal clinically important difference (MCID) for improvement of 14.48²⁷ will be used as a benchmark.

Pain

The WOMAC-Pain is a 5-item survey that prompts the respondent to reflect on the quality of pain in 5 activities during the last 48 hours²⁶. Scores range from 0 to 20, with high scores indicative of worse pain²⁶, and the MCID of 8.74²⁷ will be used as an indicator of improvement in our study.

Walking Performance

Walking performance will be evaluated by gait speed and walking endurance. All subjects will wear the Cionic Neural Sleeve during the walking tests, and all subjects will perform the same number of tests. The control group will perform the walking tests in unstimulated conditions. Unstimulated conditions require subjects to wear the Cionic Neural Sleeve as they traverse to collect EMG/kinematic data, but stimulation will not be enabled. Subjects assigned to receive the stimulation intervention will perform the walking tests in unstimulated conditions before traversing in stimulated conditions. Stimulated conditions require subjects to wear the Cionic Neural Sleeve and receive stimulation assistance while walking.

Gait speed (m/s) will be measured using the 10mWT on a 10-meter walkway with brightly colored tape to indicate boundaries, two chairs, a stopwatch/timer, and the subject's usual walking aid. During this performance test, the subject will walk with the Cionic Neural Sleeve for 10 meters, and time will be measured for the intermediate 6 meters. Two trials will be administered at the subject's comfortable walking speed, followed by two trials at fast walking speed. Rests will be provided between each trial. The trials for each speed and stimulation condition will be averaged. Acceleration and deceleration will occur outside of the timed portion to allow for a more accurate assessment²⁸. Prior literature reported an improvement of 0.12 m/s in patients with unilateral KOA post-surgery^{29,30}, and this will be used as a point of comparison in our study.

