Appendix F: Western Ontario/McMaster Universities Osteoarthritis Index (Pain)

Think about the pain you felt in your knee during the last 48 hours.

Question: How much pain do you have?

	None	Mild	Moderate	Severe	Extreme
Walking on a flat surface	█	█	█	█	█
Going up and down stairs	█	█	█	█	█
At night while in bed, pain disturbs your sleep	█	█	█	█	█
Sitting or lying	█	█	█	█	█
Standing upright	█	█	█	█	█

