Appendix H: 6-Minute Walk Test

1. A “warm-up” period before the test should not be performed.
2. The patient should sit at rest in a chair, located near the starting position, for at least 10 minutes before the test starts.
3. During this time, check for contraindications, and make sure that clothing and shoes are appropriate.
4. Instruct the subject as follows:

“The object of this test is to walk as far as possible for 6 minutes. You will walk back and forth in this hallway. Six minutes is a long time to walk, so you will be exerting yourself. You will probably get out of breath or become exhausted. You are permitted to slow down, to stop, and to rest as necessary. You may lean against the wall while resting, but resume walking as soon as you are able.

You will be walking back and forth around the cones. You should pivot briskly around the cones and continue back the other way without hesitation. Now I’m going to show you. Please watch the way I turn without hesitation.”

Demonstrate by walking one lap yourself. Walk and pivot around a cone briskly.

“Are you ready to do that? I am going to use this counter to keep track of the number of laps you complete. I will click it each time you turn around at this starting line. Remember that the object is to walk AS FAR AS POSSIBLE for 6 minutes, but don’t run or jog.

Start now, or whenever you are ready.”

5. Position the patient at the starting line. You should also stand near the starting line during the test. Do not walk with the patient. As soon as the patient starts to walk, start the timer.
6. Do not talk to anyone during the walk. Use an even tone of voice when using the standard phrases of encouragement. Watch the patient. Do not get distracted and lose count of the laps. Each time the participant returns to the starting line, click the lap counter once (or mark the lap on the worksheet). Let the participant see you do it. Exaggerate the click using body language, like using a stopwatch at a race.
7. Record the number of laps from the counter.
8. Record the additional distance covered (the number of meters in the final partial lap) using the markers on the wall as distance guides. Calculate the total distance worked, rounding to the nearest meter.
9. Congratulate the patient on good effort and offer a drink of water.

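### WOMAC-Pain and WOMAC-PF are completed after physical testing, and WOMAC-Pain after a walk stimulated only in stimulation-assigned participants; this may add noise to both scales and an arm-dependent influence to WOMAC-Pain

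*Combined protocol and SAP*

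**What the plan says.** All places are in the combined protocol and SAP.

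- **Lab Visits** gives one order for the lab visits. Maximal quadriceps testing comes first, then "FTSST, 10mWT, WOMAC-PF, 10mWT, WOMAC-pain, 6MWT, Short Form-36, and 6MWT". It specifies no rest before a questionnaire; staff check from time to time whether a break is needed.
- **Overview of Study** makes both scales primary: "Primary outcome measures of the study are quadriceps strength, perceived functional capacity, self-reported pain, and walking performance".
- **Walking Performance** sets the walking conditions. For stimulated participants: "Subjects assigned to receive the stimulation intervention will perform the walking tests in unstimulated conditions before traversing in stimulated conditions". For controls: "The control group will perform the walking tests in unstimulated conditions". The number of tests is equal across arms: "all subjects will perform the same number of tests".
- **Appendix F** opens WOMAC-Pain with "Think about the pain you felt in your knee during the last 48 hours". Appendix E uses the same 48-hour window for WOMAC-PF.
- **Table 2** gives NMES+ unstimulated walking in the programme. Whether NMES+ participants walk with stimulation in the lab is not stated.
- **Table 1** lists random assignment after the baseline measurements. Participation Selection and Randomization has everyone receive the assigned intervention at the first visit, and Lab Visits lets stimulation in the walking tests depend on group. Whether any baseline walk is stimulated is therefore unclear.

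**The concern.** WOMAC-PF and WOMAC-Pain are meant to show what a 12-week home programme does to function and pain. In the stated order, participants fill them in after physical tests that load the knee, and some items name what they have just done: rising from sitting and walking on flat surfaces (Appendix E), walking on a flat surface and standing upright (Appendix F). Symptoms provoked by the tests could enter the answers.

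For WOMAC-Pain there is a second issue. The task immediately before it differs by arm. Participants know whether stimulation is on and rate their own pain. The protocol itself lists discomfort, muscle fatigue and anxiousness as risks of stimulation, and possible pain improvement as a benefit of stimulated walking, so an acute influence could go either way. If there is one, the follow-up comparison mixes a same-day effect of the test session with the programme effect. The plan collects no pre-test WOMAC at those visits with which to separate them.

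**Working it through.** **1. Which walk precedes which form.** Lab Visits lists two 10mWTs and then two 6MWTs. Walking Performance puts the unstimulated condition before the stimulated one. Together these make the second test of each pair the stimulated one. This is an inference from two sections, but a firm one.

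| Form | Done before it at the same visit | Stimulated walk already done? |
|---|---|---|
| WOMAC-PF | strength test, FTSST, first 10mWT | no, in any arm |
| WOMAC-Pain | the same, plus second 10mWT | controls no; NMES+FES yes; NMES+ unclear |

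An acute arm-dependent influence from the visit's stimulated walk can therefore reach WOMAC-Pain but not WOMAC-PF.

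**2. Load before WOMAC-Pain.**
- Maximal contractions: 3 × 2 legs = 6, plus warm-ups. Appendix D gives 10 and 5 warm-up repetitions, so up to (10 + 5 + 3) × 2 = 36 contractions. The Quadriceps Strength section gives no warm-up repetition counts.
- Sit-to-stands: 5.
- 10-metre walks: 2 tests × (2 comfortable + 2 fast) = 8.
- Stimulated in stimulation-assigned participants: 4 walks × 10 m = 40 m.

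The number of tests is the same in every arm, so what differs between arms is the stimulation during those 40 m.

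**3. That exposure against the recall window.** At an assumed 0.8 to 1.4 m/s, 40 m takes 40/1.4 = 29 s to 40/0.8 = 50 s. The Appendix B calendar has 20-minute walks at week 6 and 30-minute walks at week 12, on three days a week. Against one 20-minute walk (1,200 s) the lab exposure is 29/1,200 = 2.4% to 50/1,200 = 4.2%. For an adherent participant, the 48 hours will usually already include programme sessions.

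**4. Scale of a possible shift.** WOMAC-Pain has 5 items scored 0 to 4, so it runs from 0 to 20. One category on two items is 2/20 = 10% of the scale. A shift of 0 to 2 points is an assumption. The documents give no figure and no standard deviation, so points cannot be converted to SD units.

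**5. What a shift would do.** The plan has no figure for the order of tasks. The nearest benchmark is the Appendix A effect size for pain, 0.41. It reproduces as a two-group standardised difference: n per group = 2(1.960 + 0.842)²/0.41² = 93.4, rounded up to 94, as stated there.

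Assume no true treatment effect, a two-sided 5% t-test without multiplicity correction, n analysed per arm, and one arm shifted by d SD. Then T is noncentral t with 2n − 2 degrees of freedom and noncentrality d√(n/2). For n = 15 the critical value is 2.048, and at d = 0.41 the noncentrality is 0.41 × √7.5 = 1.12. For the three-arm ANOVA with 15 per arm, the noncentrality is 15 × (2/3)d² = 10d², whether one or both stimulated arms are shifted.

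| Assumed shift d (SD) | t-test, 15 per arm | t-test, 10 per arm | ANOVA, 15 per arm |
|---|---|---|---|
| 0.1 | 5.8% | 5.5% | 5.7% |
| 0.2 | 8.3% | 7.1% | 7.9% |
| 0.3 | 12.5% | 9.7% | 11.8% |
| 0.41 | 19.2% | 14.0% | 18.4% |
| 0.5 | 26.2% | 18.5% | 25.7% |

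Fifteen per arm is 45/3 and assumes equal allocation, which the plan does not state; 10 per arm illustrates dropout.

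**6. Role of baseline.** If no baseline walk is stimulated, only weeks 6 and 12 carry the influence, and the paired before/after test absorbs it. If baseline walks are stimulated, a stable influence would cancel in change scores, but baseline WOMAC-Pain would then be a post-stimulation value. Data Analysis/Statistical Analysis does not say whether the ANOVA across conditions uses change or follow-up values.

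**The case against.** The strongest reply is that nothing in the documents shows an effect. The forms ask about 48 hours, not about pain now, and under a minute of stimulated walking is small beside the home programme. In NMES+FES, stimulated walking within the recall window is the treatment itself. The test load is the same in all arms and the order the same at each visit, so a common increment largely cancels in between-arm and before/after comparisons. Expectation would colour self-rated pain wherever the form sits, because after weeks of home use participants know whether they receive stimulation.

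Most of this stands. It limits the likely size and leaves test-provoked symptoms mainly as noise, unless tolerance of the tests changes with treatment. It does not exclude an influence: the tests fall inside the recall window, the preceding task differs by arm, and no separation before the form is specified.

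A reader might infer that both primary scales are biased by arm, or that no analysis could ever remove the bias. The documents support neither. WOMAC-PF precedes any stimulated walk of the visit, and a stable influence on WOMAC-Pain could cancel in change scores if baseline is also stimulated.

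**Conclusion.** The concern holds as a risk, with moderate confidence. The order may add test-provoked noise, largely common to all arms, to both WOMAC scales. It may also add a brief arm-dependent influence of unknown sign to WOMAC-Pain, in NMES+FES and possibly in NMES+. A shift of 0.1 SD would matter little (5.8% against a nominal 5%); one of 0.41 SD would raise the error nearly fourfold (19.2%). Those rates rest on assumed shifts, 15 analysed per arm and no multiplicity correction. The documents do not indicate where in that range the truth lies, and the short exposure and 48-hour recall point towards the small end.

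It would be tempting to call this a demonstrated flaw that invalidates a primary outcome. The documents do not go that far. It should be fixed because the influence, if present, is hard to separate once the data are collected, and the remedy is cheap.

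**What to change.** In Lab Visits, have participants complete WOMAC-PF and WOMAC-Pain at the start of all three visits, before strength testing and before any stimulation. Replace the two vacated breaks with seated rest of equal length in all arms. Leave the order of the physical tests unchanged, and keep the SF-36 between the two 6MWTs; it is secondary and largely uses a four-week recall.

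The cost is a one-sentence protocol change and a few minutes of rest within the 90-minute visit, with no added participants, staff or procedures. The break before the first 6MWT is already provided for, since Appendix H requires: "The patient should sit at rest in a chair, located near the starting position, for at least 10 minutes before the test starts".

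The change removes the same-visit exposure for both scales, whichever way the documents are read on baseline and on NMES+ lab walks. Those passages (Lab Visits, Walking Performance, Tables 1 and 2) still need to be reconciled for the walking outcomes. The change does not remove the general expectation effect in unblinded participants.
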